11.2. Adverse Events

Adverse events reported after the initial dose of cefiderocol will be considered treatment-emergent adverse events (TEAEs).

Adverse events will be collected from the time signed informed consent is obtained through the EOS visit or 28 (+ 7) days after administration of the last dose of the study drug. If a subject withdraws early from the study or is prematurely discontinued from study drug by the investigator, the investigator will make an effort to collect AEs for 28 days after the last dose of the study drug.

Treatment emergence will be determined by comparing the onset date with the actual date of dosing.

Adverse events will be classified by System Organ Class and PT using MedDRA Version 19.1 or higher.

All AEs will be listed by subject and chronologically by date and time of AE onset. This listing will include all data collected in the eCRF and the coded variables. Additional listings of treatment-emergent SAEs, study-drug related TEAEs, TEAEs leading to study drug withdrawal, and deaths will be provided.

11.2.1. Summaries of Adverse Events

Unless otherwise noted, TEAEs will be used for the safety analysis summaries. The following tables will be provided:

- An overall summary of the number and percentage of subjects who experience at least 1 TEAE, treatment-emergent SAE, TEAE leading to study drug withdrawal, and TEAE leading to death will be presented. The number of TEAEs, which will be counted by cases reported, will also be presented.
- TEAEs overall and by System Organ Class and PT, presenting the number and percentage of subjects with TEAEs by System Organ Class and PT. In the summary table, System Organ Class and PT within System Organ Class will be sorted by decreasing frequency. Subjects will be

This document is confidential.

counted only once in the number of subjects for this PT and only once for the number of subjects for the System Organ class to which this PT belongs (if multiple occurrences of the same System Organ Class or PT are recorded).

- Serious TEAEs, Treatment-related TEAEs, treatment-related serious TEAEs, nonserious TEAEs, TEAEs leading to study treatment withdrawal, and TEAEs leading to death will be summarized in similar way.
- TEAEs by maximum severity, overall, and by System Organ Class and PT, presenting the number and percentage of subjects with TEAEs by System Organ Class, PT, and maximum severity. If multiple TEAEs of the same PT occur within a subject, only the maximum severity observed for this PT with a System Organ Class will be used in summary of TEAEs by maximum severity, missing severity will be assumed as “severe”.. Severity will be classified into 3 categories: mild, moderate, and severe.

11.3. Laboratory Evaluations

Clinical laboratory tests will be performed at prespecified time points per the Time and Events Schedule in Appendix 1 of the protocol.

Routine hematology, blood chemistry, and urinalysis parameters that will be assessed are presented in Table 11-1.

This document is confidential.

Table 11-1 Routine Laboratory Tests

Category	Evaluation Parameters	
Hematology tests	Hematocrit Hemoglobin Platelet count	White blood cell count Differential white blood cell count
Blood chemistry tests	Aspartate aminotransferase Alanine aminotransferase Gamma glutamyltransferase Alkaline phosphatase Direct* and total bilirubin Indirect bilirubin* Total protein Albumin	C-reactive protein Blood urea nitrogen Serum creatinine Blood glucose Uric acid Electrolytes (sodium, potassium, chloride, calcium, magnesium, and bicarbonate)
Urinalysis	Microscopic analysis Protein Glucose Bilirubin	Urobilinogen Occult blood Leukocyte esterase

* If clinically indicated

Estimated GFR (eGFR) will be measured as noted below at Screening and predose if more than 24 hours after Screening) for subjects in the single-dose phase. In the multiple-dose phase, eGFR will be estimated at Screening and daily during treatment, if clinically indicated. Dose adjustments will be made following the recommendations in Table 3-4.

Estimated GFR

For ages ≥ 3 months to < 1 year, the eGFR will be based on the Schwartz equation (1984)²:

$$\text{eGFR} = 0.45 \times (\text{height}/\text{Scr}), \text{ if height is expressed in centimeters}$$

For ages ≥ 1 year to < 18 years, the eGFR will be based on the modified Bedside

Schwartz equation (2009)

$$\text{eGFR} = 0.413 \times (\text{height}/\text{Scr}), \text{ if height is expressed in centimeters}$$

OR

$$41.3 \times (\text{height}/\text{Scr}), \text{ if height is expressed in meters}$$

$$\text{eGFR (estimated glomerular filtration rate)} = \text{mL/min}/1.73 \text{ m}^2$$

This document is confidential.

Scr (standardized serum creatinine) = mg/dL

A list of the reference ranges for all clinical laboratory tests conducted will be provided by the study site prior to initiation of the study and updated by the study site if changes to the reference ranges are implemented during the study conduct.

The investigator or subinvestigator will assess whether any abnormal changes from Screening (within 48 hours prior to the administration of the first dose of cefiderocol) are clinically significant.

Laboratory test results will be assigned a Low/Normal/High (LNH) classification according to whether the value is below (L: low), within (N: normal), or above (H: high) the laboratory parameter's normal range; categorical laboratory test results will be classified as normal (N) or abnormal (A).

Summary statistics for laboratory test data (hematology, blood chemistry, and other specialized tests) will be presented for each scheduled time point measured after the first infusion and for the change from baseline to each time point. All clinical laboratory summaries other than specialized tests will be based on the local laboratory measurements, and only the data that can be converted into standard units will be included in analysis. The number and percentage of subjects with the following prespecified outlier category listed in Table 11-2 below at each postbaseline visit, including unscheduled visits, will be presented by cohort.

Table 11-2 The Outlier for Each Parameter in Laboratory Test

Parameter (Unit)	Outlier Category
Hemoglobin (g/dL)	Decrease from baseline ≥ 1.5 g/dL
Platelet count ($10^3/\mu\text{L}$)	Decrease from baseline $\geq 25\%$ and value $< \text{LLN}$ Increase from baseline $\geq 100\%$ and value $> \text{ULN}$
White blood cell count ($10^3/\mu\text{L}$)	Decrease from baseline $\geq 50\%$ and value $< \text{LLN}$ Increase from baseline $\geq 20\%$ and value $> \text{ULN}$
ALT (U/L)	Value $> 3 \times \text{ULN}$ Value $> 5 \times \text{ULN}$ Value $> 10 \times \text{ULN}$ Value $> 20 \times \text{ULN}$
AST (U/L)	Value $> 3 \times \text{ULN}$ Value $> 5 \times \text{ULN}$ Value $> 10 \times \text{ULN}$ Value $> 20 \times \text{ULN}$
AST (U/L) or ALT (U/L)	Value $> 3 \times \text{ULN}$ Value $> 5 \times \text{ULN}$ Value $> 10 \times \text{ULN}$ Value $> 20 \times \text{ULN}$
Total bilirubin (mg/dL)	Value $> 2 \times \text{ULN}$ Increase from baseline $\geq 50\%$ and value $> \text{ULN}$
Blood urea nitrogen (mg/dL)	Increase from baseline $\geq 50\%$ and value $> \text{ULN}$
Serum creatinine (mg/dL)	Increase from baseline ≥ 0.3 mg/dL
ALP (U/L)	Increase from baseline $\geq 50\%$ and value $> \text{ULN}$
AST (U/L) or ALT (U/L) + total bilirubin (mg/dL)	(AST $> 3 \times \text{ULN}$ or ALT $> 3 \times \text{ULN}$) and (total bilirubin $> 2 \times \text{ULN}$)

ALP = alkaline phosphatase; ALT = alanine transaminase; AST = aspartate transaminase; LLN = lower limit of normal; UN = upper limit of normal

This document is confidential.

Baseline will be the last value obtained prior to study drug administration within each respective phase of the study.

The eGFR and microbiology data (urine and blood collection of microbiological cultures) will be listed.

The urine pregnancy test will be performed for sexually active females of childbearing potential only. The pregnancy test results will be listed.

All serum chemistry, hematology, and urinalysis results in international standard units will be presented in data listings, with any abnormal findings appropriately flagged.

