A cUTI is defined as a clinical syndrome characterized by pyuria and a microbial pathogen in the urine in the context of the following underlying features: recurrent urinary tract infections (2 or more in a 12-month period); obstructive uropathy; a functional or anatomical abnormality of the urinary tract, including anatomical malformations or neurogenic bladder; vesicoureteric reflux; urinary tract catheterization; an invasive urogenital procedure, such as cystoscopy or urogenital surgery; or azotemia caused by intrinsic renal disease. In addition, pediatric subjects should have at least 2 of the following signs and symptoms depending on their age:

For subjects < 2 years of age

Fever defined as body temperature $\geq 38.0^{\circ}\text{C}$, failure to thrive, recent weight loss, irritability, poor feeding, lack of normal level of activity, abdominal pain/tenderness on physical examination, vomiting, or jaundice

For subjects ≥ 2 to < 18 years

Fever defined as body temperature $\geq 38.0^{\circ}\text{C}$, chills or rigors, dysuria, urinary urgency, urinary frequency, new-onset urinary incontinence, suprapubic pain, flank pain, abdominal pain, pelvic pain, suprapubic tenderness or costovertebral angle tenderness on physical examination, nausea, or vomiting

Hospital-acquired pneumonia is defined as an acute infection of the pulmonary parenchyma associated with clinical signs and symptoms, such as fever or hypothermia, chills, rigors, cough, purulent sputum production, chest pain, or dyspnea, accompanied by the presence of a new or progressive infiltrate on a chest radiograph in a patient hospitalized for more than 48 hours or developing within 7 days after discharge from a hospital. Patients with HAP may or may not require intubation and mechanical ventilation.

Ventilator-associated pneumonia is defined as an acute infection of the pulmonary parenchyma associated with clinical signs and symptoms, such as fever or hypothermia, chills, rigors, purulent respiratory secretions, and increased oxygen requirements. These signs and symptoms are in addition to laboratory abnormalities, such as leukocytosis accompanied by the presence of a new or progressive infiltrate on a chest radiograph in a patient on mechanical ventilation for a minimum of 48 hours.

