4.5 Withdrawal of Subjects from the Study or Discontinuation from Study Treatment

Withdrawal or discontinuation is defined as subjects who provide assent and/or whose parent(s)/LAR(s) provide consent to participate in the study but, the subject or parent/LAR wish to stop their participation in the study, or in the investigator's opinion, the safety of the subject is at risk.

The investigator will make every reasonable attempt to complete the study for each study subject. A subject may withdraw assent to participate in the study or a subject's parent(s)/LAR may withdraw consent for the subject's participation in the study at any time, for any reason.

The investigator or subinvestigator may discontinue a subject from study treatment at any time for any of the following reasons:

- A serious or intolerable AE occurs and the investigator or subinvestigator considers that the subject should discontinue study treatment
- Progression of the study-qualifying infection (poor or no response, aggravation, or relapse of current infection) for which the investigator considers that the subject should discontinue study treatment
- The subject recovers from the infection and antibiotic treatment is no longer required
- The subject is proven to be ineligible for the study after dosing/entry into the study
- The investigator or subinvestigator determines that the subject should be discontinued from the study treatment based on the management and discontinuation criteria for abnormal liver function tests ([Appendix 2](#))
- The study is prematurely terminated
- The investigator or subinvestigator determines that the subject should be discontinued from study treatment for any other reasons

In the event a subject withdraws assent, and/or a subject's parent(s)/LAR withdraws consent, the subject will be discontinued from the study and no further assessments will be done. However, in the event a subject is prematurely discontinued from study treatment by the investigator or subinvestigator but assent and consent from the study have not been withdrawn, EOT (or early termination) procedures including physical examination, vital sign measurements, and clinical laboratory tests will be performed and the reporting of AEs will be obtained until the EOS visit (28 [+ 7] days after administration of the last dose of study treatment).

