Appendix 2 Management and Discontinuation Criteria for Abnormal Liver Function Tests

Management and Discontinuation Criteria for Abnormal Liver Function tests have been designed to ensure subject safety and evaluate liver event etiology. (See Guidance for Industry Drug-Induced Liver Injury: Premarketing Clinical Evaluation, FDA: Jul 2009) [8].

Abnormal Liver Chemistry Criteria

The investigator or subinvestigator must review study subject laboratories to identify if any levels meet the following criteria:

- a. Aspartate aminotransferase (AST) or alanine aminotransferase (ALT) $> 5 \times$ upper limit of normal (ULN)
- b. AST or ALT $> 3 \times$ ULN and total bilirubin (TBL) $> 2 \times$ ULN or PT-INR > 1.5 , if PT-INR is measured
- c. AST or ALT $> 3 \times$ ULN with signs or symptoms compatible with hepatitis or hypersensitivity (eg, fatigue, nausea, vomiting, right upper quadrant pain or tenderness, jaundice, fever, rash, eosinophilia [$> 5\%$])

Action to be taken by Investigator

If any one of abnormal liver chemistry criterion is met, the investigator or subinvestigator must do the following:

- Subjects must be instructed to discontinue study immediately. The investigator or subinvestigator should not re-challenge the subject with the investigational product without consulting the sponsor.
- Following the initial observed elevation, every effort should be made to have the subject reassessed within 48 to 72 hours to repeat liver function chemistries and for further hepatic evaluation.
- Every effort should be made to have the subjects monitored 2 to 3 times per week until liver function chemistries (ALT, AST, alkaline phosphatase [ALP], TBL) resolve, stabilize, or return to within the normal range or to baseline levels.
- This event must be reported to the sponsor as soon as possible but no later than 72 hours of learning after its occurrence on the Liver Event Form in the eCRF.
- Consultation with a specialist such as a hepatologist is considered.
- Liver imaging (ie, ultrasound, magnetic resonance imaging (MRI), computerized tomography) is considered.

For criterion b, the case must be reported as an SAE.

If laboratory values are normalizing, follow-up reports with these values are required once the values have normalized.

If the laboratory values are significantly worsening, follow-up reports are required each time the subject is monitored for these values, ie, 2 to 3 times per week.

Follow-up Examination

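### SAP Table 11-2 counts 14 of its 16 liver outlier categories without reference to baseline, so a pre-existing elevation that is improving is counted like a new one

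*SAP*

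**What the plan says.** SAP 11.3 will tabulate by cohort "The number and percentage of subjects with the following prespecified outlier category listed in Table 11-2 below at each postbaseline visit, including unscheduled visits". In Table 11-2 the haemoglobin, platelet, white cell, urea nitrogen and creatinine categories all require a change from baseline. So do ALP and the second of the two bilirubin categories (a rise of at least 50% to a value above ULN). The ALT, AST and AST-or-ALT rows are plain multiples of ULN (above 3, 5, 10 and 20). The first bilirubin category (above 2 x ULN) and the combined transaminase-plus-bilirubin row are also absolute.

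None of the 15 exclusion criteria in Protocol 4.3 sets an ALT, AST or bilirubin limit. The nearest are shock, multiorgan failure and investigator judgement. The study is single-arm, and safety is a primary objective.

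SAP 11.3 also summarises change from baseline at scheduled time points and lists all chemistry results with abnormal values flagged. The SAP's index of tables has an outlier table by visit (14.3.4.1.4) and a chemistry change table (14.3.4.1.2). It has no shift table.

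Protocol Appendix 2 sets three liver criteria, none with a baseline term. If any is met, "Subjects must be instructed to discontinue study immediately". Protocol 4.5, which cites Appendix 2 among its reasons for stopping, begins: "The investigator or subinvestigator may discontinue a subject from study treatment at any time for any of the following reasons".

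**The concern.** With no concurrent control, each child's own pre-dose value is the main internal comparator for laboratory safety. Table 11-2 uses it for blood counts and renal function but drops it for transaminases and for the combined row. The study enrols children with sepsis, bloodstream and intra-abdominal infection, so some may have abnormal liver tests before the first dose, and the protocol lets them in.

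The outlier table covers postbaseline visits only, so a reader cannot tell from it whether a child above 3 x ULN arrived that way. Change-from-baseline summaries do not fully close the gap. They cover scheduled time points, whereas the outlier counts also take in unscheduled results, and Protocol 7.5.3 collects extra routine-care results in the multiple-dose phase. In cohorts of 6 or 10, a single child can set the percentage a reader remembers.

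**Working it through.** The plan states no outlier rate, so there is no figure of that kind to reproduce. The one related count is the minimum enrolment in Protocol 3.1: 4 x 6 + 3 x 10 = 24 + 30 = 54, which agrees.

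**Step 1. Classify the liver categories in Table 11-2.**

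| Row | No baseline term | Baseline term |
|---|---|---|
| ALT | 4 | 0 |
| AST | 4 | 0 |
| AST or ALT | 4 | 0 |
| Total bilirubin | 1 | 1 |
| ALP | 0 | 1 |
| AST/ALT plus bilirubin | 1 | 0 |
| Total | 14 | 2 |

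The haematology and renal categories (haemoglobin 1, platelets 2, white cells 2, urea nitrogen 1, creatinine 1; total 7) all have a baseline term.

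**Step 2. Run hypothetical courses (multiples of ULN) through the rules.** A category is newly crossed if the postbaseline value is above the threshold and the baseline value was not.

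| Course | Change | Counted now | Newly crossed |
|---|---|---|---|
| AST/ALT 8 to 6 | 6/8 - 1 = -25% | >3, >5 | none |
| AST/ALT 6 to 4 | 4/6 - 1 = -33% | >3 | none |
| AST/ALT 4 to 3.2 | 3.2/4 - 1 = -20% | >3 | none |
| AST/ALT 0.8 to 4 | 4/0.8 - 1 = +400% | >3 | >3 |
| AST/ALT 5.1 to 9.9 | 9.9/5.1 - 1 = +94% | >3, >5 | none |
| Bilirubin 4 to 3 | 3/4 - 1 = -25% | >2 | none |

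The 6-to-4 and 0.8-to-4 courses look identical in the current table. The 8-to-6 course also meets Appendix 2 criterion a (above 5 x ULN) while improving. The 5.1-to-9.9 course shows that newly crossed counts alone would miss real worsening.

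**Step 3. Weight of one child.** 1/10 = 10 points (exact 95% interval 0.3% to 44.5%); 1/6 = 16.7 points (0.4% to 64.1%). Cohort sizes are minimums, so a larger cohort dilutes this. SAP 6.1 uses nonmissing values as the default denominator, so missing results enlarge it.

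**Step 4. How often might it arise?** The documents give no prevalence. Let p be an assumed share of children entering above 3 x ULN. The chance of at least one in a cohort of n is 1 - (1 - p)^n.

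| p | n = 6 | n = 10 | Expected among 54 |
|---|---|---|---|
| 2% | 11% | 18% | 1.1 |
| 5% | 26% | 40% | 2.7 |
| 10% | 47% | 65% | 5.4 |
| 20% | 74% | 89% | 10.8 |

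These are upper limits on the problem under each assumption, because a child is counted only at visits where the value is still above the threshold.

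**Step 5. Which baseline?** SAP 6.2.1 uses the last laboratory value within 4 days before Treatment Day 1 or on Day 1 (single-dose), and within 4 days before Day 1 or at Screening (multiple-dose). SAP 11.3 uses the last value before study drug within each phase. SAP 11.3 also describes the Screening reference for judging abnormal changes as within 48 hours of the first dose, where Protocol 7.5.3.1 says 4 days. A pre-dose Day 1 sample in the multiple-dose phase can be baseline under one rule and not under another.

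**Step 6. Appendix 2 beside the other sections.** Appendix 2 is mandatory where Protocol 4.5 is permissive. Protocol 7.5.4.6 opens by asking about results that are new or worse than baseline after exposure. It then lists any result meeting Appendix 2 as clinically significant, and so to be recorded as an AE. Appendix 2 further requires criterion b to be reported as an SAE. Since the Appendix 2 triggers ignore baseline, the handling of an unchanged pre-existing elevation is left open.

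**The case against.** The strongest reply is that nothing is lost. Change from baseline is summarised for chemistry, every result is listed, and in cohorts this small a fall from 6 to 4 x ULN can be read from the listing. The outlier table is by visit, so that child leaves the above-5 row. AEs are framed as new or worsening events, and causality is judged separately. The absolute thresholds are also useful because several match Appendix 2 and show who reached a protocol criterion. All of this stands. It limits the point to what the summary table conveys and argues for keeping the absolute rows.

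Several stronger readings are tempting, but the documents do not support them:

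- *All liver rows ignore baseline.* ALP and the second bilirubin row use it.
- *The table counts drug effects.* It attributes no cause; a reader may do so because there is no control arm.
- *A genuine new rise cannot be separated.* The change summaries and listings allow it.
- *The infection definitions contradict Appendix 2.* Criterion c lists "fatigue, nausea, vomiting, right upper quadrant pain or tenderness, jaundice, fever, rash", and the cUTI signs under 2 years in Protocol 4.3 include "abdominal pain/tenderness on physical examination, vomiting, or jaundice". Shared signs are not a contradiction: criterion c also needs AST or ALT above 3 x ULN and signs compatible with hepatitis or hypersensitivity. Table 11-2 contains no symptoms at all.
- *Appendix 2 removes children from the study.* The following lines bar re-challenge with the product and require retesting and monitoring, so in context the wording means study treatment. Under Protocol 4.5 such children keep end-of-treatment procedures and AE follow-up, and they remain in the Safety Population. In the single-dose phase no further doses are at stake.
- *An assumed 10% to 20% with abnormal tests means 3 to 6 of 30 miscounted.* Abnormal is not the same as above 3 x ULN and still above it after dosing.

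**Conclusion.** The point holds as a reporting gap that should be closed. For 14 of 16 liver categories, Table 11-2 cannot distinguish a new elevation from one already present and falling, eligibility does not prevent the latter, and no planned table makes the distinction. The size is 10 or 16.7 points per affected child at the minimum cohort sizes. How many children are affected rests on an entry prevalence that the documents do not give. The classification of rows and the absence of a shift table can be read directly from the SAP. The validity of the underlying data is not in question.

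The mandatory wording of Appendix 2 against the permissive wording of Protocol 4.5, and the baseline-free triggers against the new-or-worse framing of Protocol 7.5.4.6, are genuine inconsistencies. They are for the sponsor to reconcile; no clinical rule is suggested here.

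**What to change.** In SAP 11.3:

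1. Keep the absolute rows of Table 11-2 as they are. Replacing them with upward category shifts would hide courses such as 5.1 to 9.9 x ULN.
2. Add a table of baseline category by worst postbaseline category for ALT, AST, AST or ALT, bilirubin and the combined criterion, by cohort and phase, including unscheduled results. Counts of newly crossed categories among subjects not above the threshold at baseline would also serve.
3. Show subjects already above the threshold at baseline on a separate line, stating whether each rose or fell.
4. Use one laboratory baseline definition, and align SAP 6.2.1 and both statements in SAP 11.3 with it.

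The cost is one extra table, programmed on data already collected, with SAP wording settled before database lock.

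At the next protocol amendment, the sponsor should reconcile Appendix 2 with 4.5 (mandatory or permissive; study or study treatment) and with 7.5.4.6 (how an elevation present before dosing is handled).
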